Intake Visit: The PCM and CHW will meet with the participant via video visit or telephone to discuss the cancer-related pain they are experiencing (PCM), as well as obtain their SDOH background to help identify barriers that may impact their ability to access pain treatment (CHW). The PCM and CHW will work with the patient to develop an action plan to help address their pain by utilizing a "Conversation Guide" bundle developed for the study. This guide will share approved patient education materials for self-guided pain management, provide information on online tools, (such as our study website) and structure interaction between the participant and PCM/CHW. Participants will be able to receive the

Conversation Guide in a variety of formats per their preference (portal, paper mailing, web, email, etc). The conversation between the PCM and the participant will lead the PCM to make suggestions/referrals from the below Tier 1 and Tier 2 interventions, which consist of 6 treatment domains.

Tier 1
Exercise
Cognitive Behavior Therapy (CBT)
Medicine

Tier 2
Integrative Medicine
-Massage
-Acupuncture
-Mindfulness
Spiritual Support
Pain Clinic Referrals
Palliative and Spiritual Care Referrals

Planning Visit: A second visit will take place approximately 2 weeks after the intake visit, depending on the availability of the participant, PCM and CHW. In this visit, the participant will give an update on their pain and additional resources may be suggested by the PCM and/or CHW.

Final Visit: The third visit will be the final visit between the participant, PCM and CHW and will take place approximately 4 weeks after the intake (depending on patient, PCM and CHW availability). Participant progress will be reviewed, final recommendations and referrals will be made.

Participant Surveys: After a participant has completed the three visits listed above, they will be sent a short survey via email, mail or portal to give feedback about their experience. Telephone may also be used to administer the survey. This feedback may help facilitate any necessary changes for the future ASCENT trial.

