## Part 2 – Qualitative Interviews & Focus Groups

**Patient Interviews**: A subset of participants (up to 40 total) will be recruited to take part in an interview about their experience in this pilot. Our goal is to reach thematic saturation. We will assume that thematic saturation has been reached when further observations and analysis reveal no new themes. Those who are interested will meet one time with a member of our study team via telephone or video. We are seeking approval for oral consent and waiver of HIPAA for the same reasons outlined in the intervention recruitment section of this protocol. Remuneration in the amount of \$30 will be given for participation in this interview. The interview will be recorded and transcribed for data analysis purposes and stored on a secured server.

*Study Team Interviews*: Up to 15 ASCENT study interventionalists will be interviewed and asked for feedback and experiences from this pilot. Recruitment will be done via email and the oral consent document will be attached to the email. A response to the invitation to schedule an interview will be regarded as an agreement to participate. No remuneration will be given for participation.

**Provider Focus Groups**: 2-3 focus groups will take place involving up to 15 Medical Oncology providers from the participating sites in this pilot. Although there is no action required of providers in this pilot study, they can view the PCM action plan. We want to look at the impact of this additional support to patients on provider workflow and obtain feedback about what they may like to see from the future ASCENT trial (e.g., how they want to be informed when their patients are enrolled in ASCENT, what information about their patients' pain management they would like to be alerted to and how). Recruitment will be done via email and the oral consent document will be attached to the email. A response to the invitation to schedule an interview will be regarded as an agreement to participate. No remuneration will be given for participating.

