#### Measurement

## Refinement of Intervention Components:

Assessment of the usability and acceptability of specific intervention components and study processes will require data collection appropriate to these study components and will be tailored to each touchpoint. In addition to multi-stakeholder review of recorded interactions, CRC- and PCM-identified ineffective script sections, participant-reported experience, extent and nature of family/lay caregiver involvement, and fidelity checklists, touchpoint specific assessments will include:

Recruitment – proportion of opened and completed Epic questionnaires, proportion of patients calling the ASCENT 1-800 line to express interest.

Engagement and Intake Visits – proportion of patients who provide complete pain and SDOH histories, select a Tier 1 pain management option, and develop a SMART goal; proportion of patients requesting review of Tier 2 options, patient engagement with sections of the ASCENT Conversation Guide (assessed by PCMs and CHWs using 11-point numerical rating scales (NRS).

Planning Visit – proportion of patients requesting revisions to the recommended plan, proportion of patients completing SMART goal; category of pain intervention selected as initial focus of multi-modal pain care plan; type of participant-selected provider as PCM contact.

Final Visit – proportion of patients able to receive and initiate use of modality selected during the planning visit, category of barriers impeding receipt of recommended pain care, general assessment of ASCENT program (NRS).

Follow Up Visits & NRS pain surveys: Proportion of patients completing surveys by administration mode, cause of pain escalation (categorical), participant-perceived barriers (categorical).

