#### PROM collection:

The following outcome measures will be collected at baseline (after consent but required before moving on to engagement) and when patients exit the pilot study after 4-5 weeks:

Measure	Domain
Primary	
BPI SF	Pain
Secondary	
	Physical
PROMIS SF	Function
EQ-5D-3L	QoL
PHQ-2	Depression
GAD-2	Anxiety
PROMIS SF	Sleep
Mediators	
PROMIS SF	Self-efficacy

These PROM data will be collected to evaluate the completeness and fidelity of outcome collection rather than to estimate intervention effectiveness. Maximizing PROM response rates and minimizing the proportion of incomplete surveys will be a key focus during our pilot activities. We will offer multiple administration modes for study completion including EHR portal, IVR, telephone interview, and printed questionnaires. The cost and logistics vary considerably across these modes. Their use and acceptance by highly rural and Hispanic individuals has not been characterized. We will therefore query patients regarding their preferred mode during the Recruitment call. After initiating a patients preferred mode we will assess the proportion of responders. We will follow up with non-responders to encourage them to trial an alternative mode. We will capture responses rates to initial and secondary administration modes across demographically-defined subgroups. For persistent non-response, we will attempt to collect PROM data via telephone interview with a CRC.

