#### *Oualitative data*

We will incrementally and iteratively develop a coding scheme beginning with the first transcript. Categories, groups of content sharing common features, will be created and abstraction of the text will be accomplished by assigning category codes. Subcategories will be identified to further delineate the content. Finally, themes or ideas that cut across categories will be created. As new concepts emerge, they will be defined and added to the coding scheme. If data saturation is not reached we will consider the need for additional interviews.

Future trial endpoints

Primary: Brief Pain Inventory

Secondary: PROMIS Physical Function, Sleep Disturbance and Anxiety Computerized Adaptive Tests We will assess the psychometric performance of the PROM study endpoints in target subgroups. In addition to calculating descriptive statistics for primary and secondary outcomes at baseline and when participants go off study, we will graph PROM scores in aggregate and by demographically-defined subgroups to assess for ceiling and floor effects and distribution of scores across the full trait range. Although the anticipated sample sizes will be limited, 20 Hispanics and 20 rural dwellers, we will compare measures of central tendency and variance in participants' PROM scores to those reported for other cohorts and used to calculate the full trial's sample size. This will clarify the whether review of the trial's power calculation is warranted.

Effective: 9/20/2017

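### The experience survey is triggered by completing all three visits and the overall program rating is listed only at the Final Visit, so participants who stop early would be given neither; moving both to study exit is a cheap improvement.

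*Combined protocol and SAP*

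**What the plan says.** Three places matter.

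- **Experience survey.** Part 1, Participant Surveys, sends it on a condition: "After a participant has completed the three visits listed above, they will be sent a short survey via email, mail or portal". The three visits are the intake, planning and final visits. Telephone is also allowed as a mode, and the stated use of the feedback is to inform changes for the full trial.
- **Overall program rating.** Under Measurement, Refinement of Intervention Components, the Final Visit entry ends with "category of barriers impeding receipt of recommended pain care, general assessment of ASCENT program (NRS"). It is listed at no other touchpoint, and the rater is not named.
- **PROMs.** These are collected at baseline "and when patients exit the pilot study after 4-5 weeks", and the Future trial endpoints text summarizes them "at baseline and when participants go off study". Non-response has its own procedure: "For persistent non-response, we will attempt to collect PROM data via telephone interview with a CRC".

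Other sources of participant experience exist. The Measurement section also names "participant-reported experience, extent and nature of family/lay caregiver involvement, and fidelity checklists" and, for follow-up contacts, "cause of pain escalation (categorical), participant-perceived barriers (categorical"). Part 2 provides interviews: "A subset of participants (up to 40 total) will be recruited to take part in an interview about their experience in this pilot". The Intervention section asks about experience at the end of recruitment and records later calls.

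**The concern.** Acceptability in the target population is part of the Hypothesis, and the pilot exists to find out what does not fit rural and Hispanic survivors. People who stop because the language, technology or content did not suit them are well placed to say what to change. The survey trigger passes them over. This is a stated rule about who is asked, rather than an omitted detail. It means that the survey comes from people who completed all three visits, and the rating from people who reached the last one. If leavers think differently, neither summary will show it, and completers and leavers cannot be compared on either measure.

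**Working it through.** **Step 1: who gets what, following the text.**

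| Attendance | Survey triggered | Overall rating taken |
|---|---|---|
| Intake, planning and final visits | yes | yes |
| Intake and final visits, planning visit missed | no | yes |
| Stops before the final visit | no | no |

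The two measures therefore select differently: the survey needs all three visits, the rating needs only Final Visit attendance. No other section gives either measure to the people in the third row. The protocol does not expressly exclude them; their absence follows from the trigger and from the lack of any other time point.

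**Step 2: share of the sample left out.** Inputs from the documents: 40 pilot participants (Subject Information); anticipated groups of 20 Hispanic and 20 rural participants (Future trial endpoints); $20 for the survey (Remuneration). The number of early leavers, *d*, is an assumption because the documents give no dropout rate.

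Share with neither measure = *d*/40:

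- *d* = 1: 1/40 = 2.5% (or 1/20 = 5% of one group of 20)
- *d* = 2: 2/40 = 5%
- *d* = 4: 4/40 = 10%
- *d* = 8: 8/40 = 20%

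**Step 3: what this could do to a summary.** Completer-only result minus all-participant result = (*d*/40) × (completer value − leaver value). For illustration only, suppose 90% of completers are favourable:

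- Leavers also 90%: difference 0 for every *d*.
- Leavers 60%: 0.05 × 30 = 1.5 points, 0.10 × 30 = 3 points, 0.20 × 30 = 6 points for *d* = 2, 4, 8.
- Leavers 30%: 0.05 × 60 = 3 points, 0.10 × 60 = 6 points, 0.20 × 60 = 12 points.

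For a numeric rating on which leavers score 2 points lower, the mean shifts by 0.1, 0.2 or 0.4. If leavers were more favourable, the signs would reverse. None of these favourability or rating values comes from the documents.

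**Step 4: cost.** The plan's own maximum payment reproduces: 3 × $50 + $20 = $170. Added survey payments are at most *d* × $20 = $40, $80 or $160 for *d* = 2, 4, 8. Total survey payments cannot exceed the 40 × $20 = $800 due if everyone finishes. At an assumed 30 minutes of coordinator time per leaver, the added time is 1, 2 or 4 hours.

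**The case against.** The strongest reply is that nothing is decided on these two measures. The Endpoints section settles optimization by 80% Delphi agreement, the response-rate goal of more than 90% does not name the experience survey, and neither measure has a threshold. Interviews may number up to 40, equal to the whole pilot sample, with no completion requirement, and an open interview may explain early stopping better than a short survey. This stands, and it keeps the point minor. It does not remove it: interviews are for a subset, may stop at thematic saturation, and are not directed at early leavers. The recruitment query comes before any visit, and recordings cover only contacts that took place.

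A second reply concerns the PROM comparison. A reader might infer that PROMs already reach everyone who withdraws, so that only the experience measures shut leavers out. The documents do not support this. Exit at 4-5 weeks fits a scheduled exit after the Final Visit, which falls about 4 weeks after intake, and no text promises an exit contact to someone who withdraws in the first week. The PROM contact is a convenient place for the fix only if the protocol says that it includes early leavers.

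A third reply is that the rating may not come from participants. Where the Measurement section does name a rater for an NRS, at the engagement and intake visits, it is the PCMs and CHWs. This also stands, so the proposal for the rating is conditional.

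Finally, people who withdraw may decline contact. The shares in Step 2 are therefore an upper limit on what the change could recover.

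**Conclusion.** The concern holds as a minor selection limit on two acceptability measures. Early leavers would receive neither, and a participant who missed only the planning visit would not trigger the survey. Each person omitted is 2.5% of the 40; with an assumed 2, 4 or 8 leavers the share is 5%, 10% or 20%. These are shares left out, not estimates of bias, whose size and direction cannot be derived from the documents and which is zero if leavers and completers agree.

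Two stronger readings should be resisted. One is that the pilot's endpoint is biased; it rests on Delphi agreement, and the survey is described only as something that may help shape the full trial. The other is that early leavers have no voice; several other sources can partly cover them. The conclusion assumes that the survey trigger is applied as written and that the rating is taken at no time point beyond the one listed.

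**What to change.** - In Participant Surveys, change the trigger from completion of three visits to study exit for any reason.
- Offer the survey to every consented participant, at withdrawal or with the exit PROM contact, and state that this contact includes early leavers who do not decline it.
- State who gives the overall rating. If it is the participant, offer it at the same time.
- Add a not-applicable option for parts not received.
- Report the number offered and the number responding, separately for completers and early leavers. With few leavers, present their answers descriptively.
- Amend Remuneration, which ties submission of payment to study completion, so that its timing also covers people who leave early.

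The cost is the wording changes, the payments and coordinator time shown above (the time is less if combined with the PROM contact), and possibly less favourable ratings. No endpoint, sample size or study visit changes.

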#### Recruitment & Consent

Using existing Patient Reported Outcome Measure (PROM) tools, potentially eligible participants with a scheduled encounter in Medical Oncology, Hematology, or Community Medicine will be identified via an EHR report, which the study coordinator(s) will regularly pull. Those with a patient portal will be sent a study invitation via portal message prior to their encounter. Nonresponders will receive the invitation during clinical registration on an Epic Welcome tablet. Patients who do not interact with the invitation via their protal of Welcome tablet will be sent the invitation by mail. Any follow-up recruitment attempts being will be conducted via portal message, telephone, or mail. Patients who do not have a portal set up will be initially invited to participate via Epic Welcome tablet. Non responders will be approached via mail or telephone, with follow-up recruitment attempts being done via telephone. Potential participants will not be contacted more than 3 times total.

We are seeking a waiver of signed informed consent as well as a waiver of signed HIPAA for this pilot protocol consonant with our intended approach to the eventual trial. Due to the minimal risk this study poses, as well as the complexities of recruiting rural and Hispanic populations and the likelihood of including undocumented Hispanic participants, we think a waiver is justified consistent with the intent of existing regulations.

Consenting will be conducted orally, at which point the participants will be screened for inclusion and exclusion criteria. The research coordinator will administer a few IT related questions to assess technology usage and fluency.

## Part 2 – Qualitative Interviews & Focus Groups

**Patient Interviews**: A subset of participants (up to 40 total) will be recruited to take part in an interview about their experience in this pilot. Our goal is to reach thematic saturation. We will assume that thematic saturation has been reached when further observations and analysis reveal no new themes. Those who are interested will meet one time with a member of our study team via telephone or video. We are seeking approval for oral consent and waiver of HIPAA for the same reasons outlined in the intervention recruitment section of this protocol. Remuneration in the amount of \$30 will be given for participation in this interview. The interview will be recorded and transcribed for data analysis purposes and stored on a secured server.

*Study Team Interviews*: Up to 15 ASCENT study interventionalists will be interviewed and asked for feedback and experiences from this pilot. Recruitment will be done via email and the oral consent document will be attached to the email. A response to the invitation to schedule an interview will be regarded as an agreement to participate. No remuneration will be given for participation.

**Provider Focus Groups**: 2-3 focus groups will take place involving up to 15 Medical Oncology providers from the participating sites in this pilot. Although there is no action required of providers in this pilot study, they can view the PCM action plan. We want to look at the impact of this additional support to patients on provider workflow and obtain feedback about what they may like to see from the future ASCENT trial (e.g., how they want to be informed when their patients are enrolled in ASCENT, what information about their patients' pain management they would like to be alerted to and how). Recruitment will be done via email and the oral consent document will be attached to the email. A response to the invitation to schedule an interview will be regarded as an agreement to participate. No remuneration will be given for participating.

## **Intervention Fidelity**

All of the above components of the intervention are regarded as "important" but not "essential" to the patient experience in the trial. We will assess fidelity by establishing check lists of essential elements for each touchpoint along the intervention trajectory including: recruitment, intake call, unscheduled CHW contacts, planning call, and scheduled PCM check-ins. For pilot activities all contacts will be recorded. Two individuals to review transcripts of the touchpoints and document whether >95% of essential elements are present. If an encounter includes fewer that 95% of the elements, the interventionalists will review training materials and role play the touchpoint with senior ASCENT team members.

#### Measurement

## Refinement of Intervention Components:

Assessment of the usability and acceptability of specific intervention components and study processes will require data collection appropriate to these study components and will be tailored to each touchpoint. In addition to multi-stakeholder review of recorded interactions, CRC- and PCM-identified ineffective script sections, participant-reported experience, extent and nature of family/lay caregiver involvement, and fidelity checklists, touchpoint specific assessments will include:

Recruitment – proportion of opened and completed Epic questionnaires, proportion of patients calling the ASCENT 1-800 line to express interest.

Engagement and Intake Visits – proportion of patients who provide complete pain and SDOH histories, select a Tier 1 pain management option, and develop a SMART goal; proportion of patients requesting review of Tier 2 options, patient engagement with sections of the ASCENT Conversation Guide (assessed by PCMs and CHWs using 11-point numerical rating scales (NRS).

Planning Visit – proportion of patients requesting revisions to the recommended plan, proportion of patients completing SMART goal; category of pain intervention selected as initial focus of multi-modal pain care plan; type of participant-selected provider as PCM contact.

Final Visit – proportion of patients able to receive and initiate use of modality selected during the planning visit, category of barriers impeding receipt of recommended pain care, general assessment of ASCENT program (NRS).

Follow Up Visits & NRS pain surveys: Proportion of patients completing surveys by administration mode, cause of pain escalation (categorical), participant-perceived barriers (categorical).

#### PROM collection:

The following outcome measures will be collected at baseline (after consent but required before moving on to engagement) and when patients exit the pilot study after 4-5 weeks:

Measure	Domain
Primary	
BPI SF	Pain
Secondary	
	Physical
PROMIS SF	Function
EQ-5D-3L	QoL
PHQ-2	Depression
GAD-2	Anxiety
PROMIS SF	Sleep
Mediators	
PROMIS SF	Self-efficacy

These PROM data will be collected to evaluate the completeness and fidelity of outcome collection rather than to estimate intervention effectiveness. Maximizing PROM response rates and minimizing the proportion of incomplete surveys will be a key focus during our pilot activities. We will offer multiple administration modes for study completion including EHR portal, IVR, telephone interview, and printed questionnaires. The cost and logistics vary considerably across these modes. Their use and acceptance by highly rural and Hispanic individuals has not been characterized. We will therefore query patients regarding their preferred mode during the Recruitment call. After initiating a patients preferred mode we will assess the proportion of responders. We will follow up with non-responders to encourage them to trial an alternative mode. We will capture responses rates to initial and secondary administration modes across demographically-defined subgroups. For persistent non-response, we will attempt to collect PROM data via telephone interview with a CRC.

